2.6.2 Treatment for Non-Overminus Group

NOTE: Details of spectacles to be prescribed will be automatically calculated by the study website.

No IXT treatment other than the study spectacles specified below can be prescribed at any time during the study unless the subject meets deterioration criteria described in section 3.7.

Enrollment Visit

- Subjects in the non-overminus group will be prescribed spectacles based on the cycloplegic refraction as follows:
 - If the cycloplegic refraction is spherical and between plano sphere and +1.00D sphere in both eyes (with no astigmatism and no anisometropia), subjects will wear spectacles with plano lenses in both eyes to maintain masking.
 - Otherwise, fully correct the astigmatism and prescribe sphere as follows:
 - If least hyperopic eye has SE myopia:
 - Prescribe the full sphere in both eyes
 - If least hyperopic eye has SE hyperopia or emmetropia:
 - Prescribe sphere so that spectacles will have plano SE in the least hyperopic eye
 - Match any reduction of sphere made to the least hyperopic eye in the fellow eye
- Subjects will wear the new prescription all waking hours until the 12-month visit.

12-Month Visit*

- Spectacles will be updated at the 12- month visit using the same prescribing guidelines at enrollment (see above) but using the 12-month cycloplegic refraction, unless the subject has already met deterioration criteria confirmed by masked examiner as described in *section 3.7* in which case spectacles are prescribed at investigator discretion.
- To maintain masking, lenses will be replaced even if there is no change in the cycloplegic refraction.

* Unless the subject has already met deterioration criteria confirmed by masked examiner as described in section 3.7 in which case spectacles are prescribed at investigator discretion.

15-Month Visit*

- If the 12-month spectacles for a subject were issued **before** Protocol Amendment II, the non-overminus lenses should be replaced at the 15-month visit to maintain masking of treatment groups (see 12-month prescribing above).
- If the 12-month spectacles for a subject were issued **on/after** Protocol Amendment II and therefore are already non-overminus spectacles, the non-overminus spectacles should be continued at the 15-month visit.) There is no longer a reason to change the

1255	glasses to maintain masking, because both treatment groups are already wearing non-
1256	overminus glasses.
1257	*Unless the subject has already met deterioration criteria confirmed by masked examiner as
1258	described in section 3.7 in which case spectacles are prescribed at investigator discretion.

CHAPTER 3: FOLLOW-UP AND MANAGEMENT

1259 1260 1261

3.1 Follow-up Schedule

1262 The follow-up schedule is timed from randomization as follows:

- 1-Month Phone call: 3 weeks (3-4 weeks)
- 3-Month Phone call: 3 months (3-4 months)
- 6-Month Office Visit: 6 months ± 1 month
- 9-Month Phone call: 9 months (9-10 months)
- 12-Month On-Treatment Primary Outcome Visit: 12 months ± 1 month
- 13-Month Phone call: 3-4 weeks following 12-month visit)
- 15-Month Off-Treatment Interim Visit: 15 months ± 1 month
 - 16-Month Phone call: 3-4 weeks following 15-month visit)
- 18-Month Off-Treatment Primary Outcome Visit: 18 months ± 1 month

12721273

1270

Additional visits may be scheduled at investigator discretion.

1274

Subjects with a drop (worsening) of 2 or more octaves from baseline in near stereoacuity during follow-up (*see section 3.7*), confirmed by a retest on the same day, will need to return for an additional retest on a subsequent day.

1278 1279

1280

1281

1282

3.2 Telephone Calls

At each time during the study when subjects in both groups receive new study spectacles, the site will contact parents to determine whether the study spectacles (overminus spectacles/non-overminus spectacles/plano spectacles) have been dispensed/received. These calls will occur 3 weeks following the enrollment, 12-month, and 15-month visits as defined above.

1283 1284 1285

The site will record the date that the new spectacles were received or document that they have not been received as of the call date. Parents will be reminded to have their children wear the spectacles all waking hours.

1287 1288 1289

1290

1291

1286

Additional protocol-specified calls to engage the subject and encourage spectacle compliance will be made from the investigator's site at 3 months and 9 months following randomization as defined above.

1292 1293

Additional calls may be made as needed as outlined in section 4.1.

1294 1295

1296

1297

3.3 Masking of Treatment Group

Subjects will be masked to treatment group throughout the study. Subjects who do not have refractive error that requires correction (*see sections 2.6.1 and 2.6.2*) will be prescribed plano lenses if randomized to the non-overminus group.

1298 1299 1300

1301

1302

1303

1304

1305

Key outcome testing at each follow-up visit (*see section 3.3.1*) will be performed by an examiner masked to treatment group. Although the examiner will see the subject's spectacles during test, the presumption is that treatment group is unlikely to be discerned because 1) all subjects will be wearing spectacles and 2) because both treatment groups will have a range of prescriptions depending on subjects' underlying refractive error in addition to whether an overminus component is included. The Masked Examiner must be a pediatric ophthalmologist,

pediatric optometrist, or certified orthoptist. The Masked Examiner should preferably be someone *other than* the investigator.

If necessary at rare sites, the Masked Examiner may be the investigator if the investigator remains masked to the randomized treatment. At such sites, for prescription of spectacles throughout the study, the investigator should sign two prescriptions (one overminus prescription and one non-overminus prescription), after which an unmasked coordinator would provide the parent with the appropriate prescription according to the subject's treatment group.

 The investigator will be unmasked to treatment group except at rare sites in which he/she must serve as the masked examiner. The investigator should not discuss a subject's treatment group with the subject or his/her parents.

3.3.1 Masked Examiner Testing

A masked examiner will assess the following at the 6-month, 12-month, 15-month, and 18-month visits regardless of whether or not the subject has already met deterioration criteria confirmed by masked examiner as described in *section 3.7* at a previous visit:

- Control assessment #1
- Stereoacuity
- Control assessment #2
- Cover test
- 1327 PACT
 - Control assessment #3
 - Assessment of deviation throughout the exam

The Masked Examiner must not verify the spectacles using lensometry, discuss compliance of spectacle wear with the subject or parents, or administer the symptom survey. The Masked Examiner should not review the subject's medical record prior to the exam.

3.4 Outcome Visit Testing Procedures

If deterioration has NOT been confirmed by masked exam at a previous visit, subjects should be tested in study specific spectacles (i.e., overminus spectacles or non-overminus spectacles including plano spectacles). If deterioration has been confirmed by masked exam at a previous visit, subjects will be tested in their current refractive correction.

Someone *other than* the Masked Examiner will ensure that the subject is wearing the appropriate spectacles (as described above) prior to the masked exam.

Subjects not bringing their spectacles to the outcome visit (or who have had their spectacles discontinued for any reason) will be tested in trial frames. Subjects who have had their spectacles discontinued (not likely to occur) should be tested in plano trial frames. To avoid potential unmasking, the trial lenses must have wire frames (not red or black indicating minus or plus power). Care should be taken to cover any power-indicating markings with tape to ensure that masking is maintained.

The following procedures should be performed by the appropriate examiner (*see below*) and in order where specified:

- 1354 The following procedures are tested first by someone *other than* the Masked Examiner:
 - 1. Spectacle Prescription Verification (Lensometry): Prior to performing the outcome examination, the subject's spectacle correction will be verified using a lensometer (including plano lenses).
 - Spectacles should meet the following tolerances:
 - > Sphere within 0.50D of prescribed
 - > Cylinder within 0.50D of prescribed
 - > Axis within 10 degrees of prescribed
 - If spectacles do not meet these tolerances, the subject should be tested with trial frames with the intended prescription in place.
 - 2. Compliance Assessment: Compliance with spectacle wear since receiving the spectacles will be assessed based on discussion with the parents and using the following scale:
 - o Excellent (76% to 100%)
 - o Good (51% to 75%)
 - o Fair (26% to 50%)
 - \circ Poor ($\leq 25\%$)

1356 1357

1358 1359

1360

1361

1362

13631364

1365

1366 1367

1368

1369

1384

13851386

1387

1388 1389

1390

1391

1392

- 3. Health-Related Quality of Life Questionnaire and Symptom Surveys (6-month, 12-month, and 18-month visits only): The parent and child will complete the same questionnaire and symptom surveys as described at the time of enrollment.
- After the above assessments, the following procedures must be performed in the specified order by the Masked Examiner. All procedures should be performed with the subject wearing his/her current study spectacles (or trial frames if study spectacles were not brought to the visit) and without cycloplegia:
- 1377 Although tests #4 through #10 must be performed in the specified order, there is no specified 'waiting' time that needs to occur between measurements.
- 4. Control of the Exodeviation #1 (Masked): A Masked Examiner will assess control of exodeviation at distance and near fixation using the intermittent exotropia control scale.²⁸⁻³⁰
- 5. Stereoacuity Testing (Masked): Stereoacuity will be assessed using the Randot Preschool stereotest at 40 cm. If the subject has no measurable stereo, this finding will be recorded as "nil".

If stereoacuity has decreased by 2 octaves or more (see Table 2 below) from baseline:

- Stereoacuity must be retested on the same day by the masked examiner. Retesting can be performed any time after the final assessment of control (Step 10) but prior to any cycloplegia.
 - o If the stereoacuity is still reduced 2 octaves or more from baseline on the same-day retest, the subject must be brought back for a retest of stereoacuity on a different day (see section 3.5).

Table 2: Preschool Randot Stereotest

Baseline stereoacuity,	Level needed at follow-up visit					
in arcsec	to require retest, in arcsec					
40"	200", 400", 800", nil					
60"	400", 800", nil					
100"	400", 800", nil					
200"	800", nil					
400"	Nil					
800"	Nil					
Nil	Not applicable					

1399

14001401

1402

1403

14041405

1406

- 6. Control of the Exodeviation #2 (repeat) (see item #4) (Masked)
- 7. Cover Test (Masked): Assessed in primary position at distance (6 meters) and near (1/3 meter) as outlined in the IXT Testing Procedures Manual.
- 1398 8. PACT Testing (Masked): A Masked Examiner will assess:
 - PACT in primary position at distance (6 meters) and near (1/3 meter) as outlined in the IXT Testing Procedures Manual.
 - AC/A ratio (18-month visit only) at distance (6 meters) measuring the PACT with the subject wearing -2.00D lenses over his/her habitual correction. The AC/A ratio is calculated by taking the difference between the distance PACT measurements with and without -2.00D lenses and dividing the difference by 2.
 - 9. Control of the Exodeviation #3 (repeat) (see item #4) (Masked)
 - 10. Assessment of Deviation Throughout Exam (Masked)

1407 1408

The following procedures should be performed by either the Masked Examiner or another study-certified examiner:

14101411

1409

1412

1413

1414

1417

14181419

1420

1421

1422

1423

1424

- 11. Distance Visual Acuity Testing: Monocular distance visual acuity testing with the habitual correction and without cycloplegia will be measured using the same testing procedure as used for enrollment. Visual acuity may be tested at the start of the exam or before the cycloplegic refraction.
- 1415 12. Cycloplegic Autorefraction (12-month and 18-month visits only, mandatory if autorefractor is available at the site)
 - Refractive error must be measured with the same autorefractor used at enrollment following cycloplegia with 1% cyclopentolate (see cycloplegic refraction below).
 - If cycloplegic autorefraction was completed at enrollment, then it must be measured with the same autorefractor used at enrollment.
 - Regardless of whether cycloplegic autorefraction was completed at enrollment, it is mandatory to measure cycloplegic autorefraction if an autorefractor is available at the site.
 - Recorded values will be based on a single measurement by the instrument (which may be a mean of several individual measures depending on system)
- 1426 13. Cycloplegic Axial Length Measurement and Additional Biometry (18-month visit only) (see manual of procedures).

• Axial length

1433 1434

1435

1436

14371438

1439

14401441

1442

1443

1444

1445

1446

1447 1448

1449 1450

1451

14521453

1454

1455

1456

14571458

1459

1460

1461

1462

1463 1464

1465

1466

1467 1468 1469

1471

- Flat corneal radius
- Anterior Chamber depth
- Lens thickness, if available
- 1432 14. Cycloplegic Refraction (12-month and 18-month visits)
 - A cycloplegic refraction will be performed at the 12-month and 18-month visits. The cycloplegic refraction will be performed regardless of whether a cycloplegic autorefraction is performed.
 - Cycloplegic refraction is performed 30 to 45 minutes following at least one application of cyclopentolate 1% per investigator's usual dosage and timing routine.
 - The cycloplegic refraction is based on cycloplegic retinoscopy, which may be done with glasses off or as an over-refraction in front of the current spectacles. Subjective refraction is allowed.
 - When an over-refraction of current eye glasses is performed, the reported cycloplegic refraction will be the sum of the current spectacle power and the over-refraction.
 - 15. ADHD and Seizure Medication Use Data Collection (12-month visit only)
 - At the 12-month visit, data regarding any ADHD and seizure medication use in the past 12 months will be collected.

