 - If prism is currently prescribed, testing should be performed *without* prism.
 - If deliberate overminus** is currently prescribed, testing should be performed in trial frames *without* the overminus component of the prescription.
 - 4. Stereoacuity Testing **masked** stereoacuity is tested only once, with no repeat testing on the same day or a subsequent day.
 - Testing must be performed in current refractive correction.
 - If prism is currently prescribed, stereoacuity testing should be performed with prism.
 - If deliberate overminus** is currently prescribed, stereoacuity testing should be performed *with* the overminus correction.
- 5. Control of the Exodeviation #2 masked see details under Control Testing #1 above
- 234 6. Cover Test and PACT Testing masked
 - Testing must be performed in current refractive correction.
 - If prism is currently prescribed, ocular alignment testing should be performed *without* prism.
 - If deliberate overminus** is currently prescribed, ocular alignment testing should be performed in trial frames *without* the overminus component of the prescription.
- 7. Control of the Exodeviation #3 - masked see details under Control Testing #1 above

- 241 8. Assessment of Deviation Throughout Exam- masked
- 242 9. Cycloplegic Refraction
- 243 11. Cycloplegic Autorefraction (mandatory if autorefractor is available at the site) as described in section 3.4
- 12. Cycloplegic Axial Length Measurement and Additional Biometry (mandatory if biometer is
 available at the site) as described in section 3.4
 - Axial length

247

248

249

251

255256

257258259

262263

264

265266

267268269

270271

272273

274

275

276277

278

279280

283

284

285 286

287

- Flat corneal radius
- Anterior Chamber depth
- Lens thickness, if available

*Deliberate overminus lenses = lenses that yield > 0.50 D *more minus* spherical equivalent (SE) than the refraction SE. Note that prescribing underplus or no plus is not considered deliberate overminus.

Steps #3 through #8 must be performed in order by a masked examiner who is a pediatric ophthalmologist, pediatric optometrist, or certified orthoptist.

Treatment

After 18 months, IXT treatment (surgical, non-surgical, management of refractive error) is at investigator discretion.

Costs

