2.6.1 Treatment for Overminus Group

NOTE: Details of spectacles to be prescribed will be automatically calculated by the study website.

No IXT treatment other than the study spectacles specified below can be prescribed at any time during the study unless the subject meets deterioration criteria described in section 3.7.

Enrollment Visit

- Subjects randomly assigned to the overminus group will be prescribed spectacles based on a cycloplegic refraction as follows:
 - o Fully correct the astigmatism in both eyes (if present)
 - Add -2.50D to the sphere component of the cycloplegic refraction for both eyes
- Overminus spectacles are prescribed to be worn all waking hours through the 12-month outcome visit.

12-Month Visit*

- At the 12-month outcome visit, overminus treatment will be discontinued and new nonoverminus spectacles will be prescribed based on the 12-month cycloplegic refraction as follows*:
 - If the cycloplegic refraction is spherical and plano or any amount of hyperopia in both eyes (with no astigmatism and no anisometropia), subjects will wear spectacles with plano lenses in both eyes to maintain masking.
 - Otherwise, fully correct astigmatism in both eyes and prescribe sphere as follows:
 - If least hyperopic eye has SE myopia:
 - Prescribe the full sphere in both eyes
 - If least hyperopic eye has SE hyperopia or emmetropia:
 - Prescribe sphere so that spectacles will have plano SE in the least hyperopic eye
 - Match any reduction of sphere made to the least hyperopic eye in the fellow eye
 - Subjects will wear the new prescription all waking hours until the 18-month visit.

* Unless the subject has already met deterioration criteria confirmed by masked examiner as described in section 3.7 in which case spectacles are prescribed at investigator discretion.

15-Month Visit*

- If the 12-month spectacles for a subject were issued **before** Protocol Amendment II and therefore contain partial-strength overminus (-1.25D), the spectacles should be changed to non-overminus spectacles at the 15-month to discontinue the overminus (see 12-month prescribing above).
- If the 12-month spectacles for a subject were issued **on/after** Protocol Amendment II and therefore are already non-overminus spectacles, the non-overminus spectacles should be continued at the 15-month visit.

* Unless the subject has already met deterioration criteria confirmed by masked examiner

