3.7 Deterioration Criteria

Subjects who meet either of the following at any visit will be considered to have met deterioration criteria.

- Motor deterioration: Control of the exodeviation measures 5 (constant exotropia) on all three assessments at distance and near. The exodeviation does not need to be constant throughout the entire exam provided that it is constant during all three control testings.
- Stereoacuity deterioration: Drop in near stereoacuity of at least 2 octaves (as defined in section 3.4) (at least 0.6 log arcsec) from enrollment stereoacuity, or to nil, confirmed by a retest by a Masked Examiner on a subsequent day (section 3.5). Note: subjects with nil stereoacuity at enrollment will not be able to deteriorate with respect to a drop in near stereoacuity.

Subjects who meet deterioration criteria may have non-randomized treatment for IXT started at investigator discretion. Whether or not a subject starts non-randomized treatment for IXT during the study, all subjects will still be followed at regular study visit intervals through the end of the study.

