3.8 Initiating Non-Randomized Treatment for IXT

Non-randomized treatment for IXT is not permitted during the study unless the subject has met deterioration criteria (*see section 3.7*). If neither deterioration criterion is met but the subject is experiencing overwhelming social concerns or significant symptoms associated specifically with the exodeviation, the investigator must call the protocol chair to discuss the case and obtain approval for an exception prior to initiating non-randomized treatment for IXT.

Non-randomized treatment for IXT refers to any treatment other than that which the subject was randomized to. It includes but is not limited to:

- 1506 Surgery
 - Occlusion
 - Vergence exercises
 - Overminus spectacles (in non-overminus group)
 - Cycloplegia

• Formal discontinuation of overminus spectacles (in overminus group) – note that subject non-compliance with overminus spectacles is not considered formal discontinuation.

If the investigator plans to initiate non-randomized treatment for IXT at an additional visit rather than a protocol-specified visit, a masked examination must be performed prior to initiating the new treatment (section 3.6).

Subjects who have started non-randomized treatment for IXT during the study will still be followed at regular study visit intervals through the end of the study.

1522 3.9 **Treatment of Amblyopia**

Given the exclusion of subjects with amblyopia, the rate of developing amblyopia during the study is expected to be low. Nevertheless, if amblyopia develops during the study, the investigator may initiate amblyopia treatment, however initiating atropine, other cycloplegic drops, or levodopa is not allowed.

1526 1527

1523

1524

1525

Management of Refractive Error

1528 Management of refractive error will follow study guidelines (see sections 2.6.1 and 2.6.2) for 1529 1530 the duration of the study. A cycloplegic refraction will be performed for all subjects at the 12-1531 month visit and the 18-month visit. These data are used to adjust the glasses at 12-,15- and 18-1532 month visits.

CHAPTER 4: MISCELLANEOUS CONSIDERATIONS

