226 12 months and weaning of overminus between 12 to 15 months. The full cohort analysis
227 will be considered the main secondary analysis. In addition, these analyses will be
228 repeated for the 18-month visit in a sensitivity analysis that will be limited to participants
229 who were prescribed full treatment and weaning, defined as those who completed their
230 15-month visit before Protocol Amendment II discontinuing overminus treatment was
231 approved by the Jaeb IRB on 12/18/19.. If retention of an on-treatment effect is stronger
232 in participants who have full treatment/weaning vs. less than full treatment/weaning, the
233 18-month treatment effect could be diluted in the full cohort analysis vs. the limited
234 cohort.

235

236 **2.2.1 Treatment Group Comparison of Mean 18-month Distance Control**

237 The analyses specified above in Section 2.1 will be repeated using the mean 18-month
238 distance control score. As per the rationale in protocol change #2 of Protocol Amendment
239 I, the 18-month comparison is a secondary analysis, hence no adjustment to alpha (5%)
240 will be made to either the primary or the secondary analyses. It is acknowledged this
241 could inflate the overall type I error rate, i.e. probability of one or more false positive
242 findings, for the analyses of these outcomes.

243

244 The treatment group comparison of mean distance control at the 18-month visit will
245 follow the same modified intention-to-treat principle as specified in Section 2.1.1. To be
246 included in the analysis, the 18-month visit must be completed no earlier than 15 months
247 and no later than 24 months after randomization. If the 18-month visit is not completed
248 within the analysis window, the distance control at the 18-month visit will be imputed
249 using multiple imputation (as specified in Section 2.1.9 above). Eighteen-month data for
250 participants in the overminus group who do not discontinue overminus spectacles
251 according to protocol will be included in analyses and will not be imputed, as will 18-
252 month data from participants in the non-overminus group who start overminus.

253
254
255
256
257
258
259
260
261
262
263
264
265
266
267
268
269
270
271
272
273
274
275
276
277
278
279
280
281
282
283
284
285
286
287
288
289
290
291
292
293
294
295
296
297
298

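### At 18 months, children with previously confirmed deterioration may be scored through overminus lenses and still count in the off-treatment comparison; the testing condition is inconsistent and no sensitivity analysis covers overminus-arm children who never stopped

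*Protocol*

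**What the plan says.** **Which spectacles are worn.** Protocol 2.6.1 and 2.6.2 set the 12- and 15-month prescriptions so that both arms end up in non-overminus lenses. They exempt children with deterioration already confirmed by a masked examiner, "in which case spectacles are prescribed at investigator discretion". Protocol 3.7 adds: "Subjects who meet deterioration criteria may have non-randomized treatment for IXT started at investigator discretion". Section 3.8 lists, among such treatments, "Overminus spectacles (in non-overminus group").

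**Which lenses are used for testing.** Protocol 3.4 has two rules. Children without previously confirmed deterioration are tested in study spectacles, or in trial frames with the intended prescription if the spectacles fail tolerance. For the rest: "If deterioration has been confirmed by masked exam at a previous visit, subjects will be tested in their current refractive correction". There is no exception for overminus and no separate rule for 18 months.

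**Which scores are analysed.** SAP 2.2.1 names "participants in the overminus group who do not discontinue overminus spectacles" and continues: "according to protocol will be included in analyses and will not be imputed". The same sentence extends this to "month data from participants in the non-overminus group who start overminus". Under SAP 2.1.1, which 2.2.1 carries to 18 months, starting a treatment other than overminus or non-overminus spectacles leads to imputation. Wearing overminus does not.

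**What the result is meant to show.** Protocol 1.15 defines the secondary objective as the off-treatment effect on distance control, after three months off treatment.

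**What happens later.** In Protocol Amendment II, Change #6, a child in deliberate overminus at 24 or 36 months has control scored differently: "testing should be performed in trial frames *without* the overminus component of the prescription". Alignment is handled in the same way.

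**The concern.** The lens used at the 18-month test depends on an earlier outcome. Only children whose deterioration was confirmed can be scored through overminus, yet their scores are averaged with those of children tested without it and the result is labelled off-treatment.

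Two results are affected: the 18-month difference in mean distance control, and the SAP 2.3 percentage of the 12-month effect retained at 18 months. An overminus-arm child scored through the lens can look like retained benefit. A non-overminus child scored through it improves the comparator.

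The 12-month primary comparison is on treatment by design, so this mismatch between label and testing condition does not arise there.

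**Working it through.** **Inputs from the documents.** Planned 18-month effect 0.65 points, SD 1.8, two-sided alpha 0.05, power 90%, losses of 10% and then a further 5% (Protocol 5.7.2); 1:1 allocation (Protocol 1.16).

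**Assumptions.** The documents do not say how many children are scored through overminus. Let fO and fN be those shares of the overminus and non-overminus arms, taken from 0 to 10%. Let L be the lens effect, set to the planned 0.65. Let R be the true retained off-treatment effect.

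**The plan's own figure.** A two-sided t-test with difference 0.65 and SD 1.8 needs 163 per arm, 326 in all (power 0.9015). Then 326 / 0.85 = 383.5, rounded up to 384. Both figures reproduce. The standard error of the difference is 1.8 × √(2/163) = 0.199.

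**Model.** A child scored through overminus contributes an effect L. Otherwise an overminus-arm child contributes R and a non-overminus child 0. The apparent effect in favour of overminus is

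R + fO × (L − R) − fN × L.

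**Case 1: no true off-treatment effect (R = 0), overminus arm only.** The shift is 0.65 × fO. Rejection rates use the normal approximation.

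| fO | Children of 163 | Shift toward overminus | Two-sided rejection rate |
|---|---|---|---|
| 1% | about 2 | 0.007 | 5.0% |
| 3% | about 5 | 0.020 | 5.1% |
| 5% | about 8 | 0.033 | 5.3% |
| 10% | about 16 | 0.065 | 6.2% |

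At 5% the shift is 0.0325 / 0.199 = 0.16 of a standard error; at 10% it is 0.33. The same shares in the non-overminus arm alone give equal shifts the other way. Equal shares in both arms cancel.

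**Case 2: full retention (R = 0.65), non-overminus arm.** The apparent effect is 0.65 × (1 − fN). At fN = 3%, 5% and 10% it is 0.63, 0.62 and 0.585, and power falls from 90% to 88.5%, 87.2% and 83.5%.

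**Case 3: retention percentage, R = 0.13 (20% of 0.65), 12-month effect held at 0.65.**
- fO = 5%, fN = 0: 0.13 + 0.05 × 0.52 = 0.156, and 0.156 / 0.65 = 24%. The gain per child is 0.65 − 0.13 = 0.52; adding the full 0.65 would count the retained part twice.
- fO = 0, fN = 5%: 0.13 − 0.0325 = 0.0975, or 15%.
- Both 5%: 0.156 − 0.0325 = 0.1235, or 19%.

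**Do the planned sensitivity analyses reach these children?** SAP 2.2.1 repeats the Section 2.1 analyses at 18 months, including #3 (last observation carried forward) and #4 (multiple imputation) for crossovers. Both are worded for children who switched before the 12-month visit. Adapted to 18 months, they can reasonably be read to include non-overminus children who start overminus. An overminus-arm child who never left overminus has not switched. The weaning-cohort analysis selects on the date of the 15-month visit and does not exclude such a child.

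**The case against.** **Inclusion is a disclosed choice.** Amendment I, Change #3, argues that analysing crossovers as observed is conservative and says similar reasoning applies at 18 months. This holds for non-overminus children who start overminus, since they dilute the difference. It does not hold for overminus-arm children still in overminus, whose inclusion favours overminus. The choice of testing lens is also separate from the choice of analysis population: every child can stay in the randomised arm and still be tested under one lens condition.

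**The affected group is narrow.** This stands. A child must have confirmed deterioration, be wearing overminus at 18 months, and not have started another treatment, which would trigger imputation. SAP 3.1 notes low deterioration rates in an earlier study. The SAP 2.2.1 sentence about not discontinuing as the protocol requires also fits poorly, since confirmed deteriorators in discretionary overminus are within protocol; they are analysed as observed by default. Children who stay in overminus without confirmed deterioration should be tested in non-overminus lenses under Protocol 3.4.

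**Stronger readings the documents do not support.**
- A reader might infer that the rule always inflates the overminus result. The sign depends on fO − fN, weighted as in the model.
- A reader might infer that it hides deterioration in the non-overminus arm. The rule applies only after deterioration is confirmed, when the event in SAP 3.1 has already been counted.
- A reader might extend the criticism to stereoacuity. The extension itself tests stereoacuity with the overminus in place, so there is no conflict.
- A reader might see a broken comparison across 18, 24 and 36 months. Control at the later visits is exploratory without p-values (SAP 5.4), so this matters little.

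**Conclusion.** The inconsistency is real. The 18-month score is defined as off treatment, yet one subgroup, selected by prior outcome, may be scored through the treatment lens, and the protocol's own 24/36-month procedure handles the same situation differently.

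The likely size is small: 0.007 to 0.065 points if 1% to 10% of the overminus arm is affected and no true effect remains, always less than a third or so of a standard error. The retention percentage is easier to misread, with 20% appearing as 24% at a 5% share. These figures rest on assumed shares and on applying the full planned 0.65-point effect to children selected for deteriorating, which may be generous.

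The point concerns the definition and interpretation of a secondary result. It does not affect the sample size or the primary analysis. It is worth correcting because the one group whose inclusion favours overminus is the group that no planned sensitivity analysis clearly covers.

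**What to change.** 1. **Testing condition.** Reconcile Protocol 3.4 with Amendment II, Change #6, so that control and PACT at 18 months are measured under the same lens condition as at 24 and 36 months. This is a measurement rule and leaves prescribing untouched. Trial frames with covered markings are already in Protocol 3.4.
2. **Count.** In SAP 2.2.1, report per arm how many children were tested through deliberate overminus at 18 months, identified from that visit's lensometry and cycloplegic refraction. Use the extension's definition (more than 0.50 D more minus than the refraction) together with its note that reduced or absent plus does not count. Otherwise a child with +1.00 D correctly wearing plano study lenses would be flagged.
3. **Sensitivity analysis.** In SAP 2.2.1 and 2.3, repeat the 18-month difference and the retention percentage with the flagged scores multiply imputed as in SAP 2.1.9. State explicitly that overminus-arm children who never discontinued are included.

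**Cost and limits.** A little extra analysis, and a lens change at the exam for any visit still to come. The last 12-month visits were planned by December 2019 and the SAP is dated February 2021, so the 18-month visits are probably over and items 2 and 3 carry the weight. Changing the testing lens removes the direct optical effect but not carry-over from continued wear, so the count is needed either way. The imputation assumes these children resemble others in their arm with similar earlier scores.
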